# Intervention

Headspace is a commercially available application which runs on all major smartphones, tablets and webbrowsers. Headspace meditation scripts are designed by [name], who has Buddhist monastic training and is a registered meditation consultant with the UK Health Commission. Headspace uses audio and visual media to guide users through mindfulness meditation practices and discussions of mindfulness-related content. Headspace offers simple, short mindfulness practices, described as 'bite size' that are not affiliated with any religion and can be accessed at any time of day, convenient to the user. The stress-reduction intervention consists of 30 ten-minute guided sessions which can be accessed through the Headspace app (or on the website). Each session begins with focusing on the breath, before gradually introducing mindfulness-relevant content and ways to apply such 'attention control' to user's day-to-day life.

Users will be given a unique ID that they can use to access the intervention once they have consented to take part in the study. Usage data will be generated for each participant, including time spent practising and sessions looked at. Any necessary agreements and contracts will be dealt with by the University of Southampton and the suitable agreement between Headspace and the University will be mutually agreed. More information about Headspace can be found here: https://www.headspace.com/how-it-works

*Blinding:* The trial co-ordinator will be un-blinded in order to complete the intervention registration procedure to grant participants free access to Headspace but all researchers involved in quantitative analysis will remind blinded to participant group.

# Assessment and follow up

**Baseline:** Consent, and validated questionnaires (see details below) will be administered online (in line with previous protocols of online consent conducted at the University of Southampton), at the end of which patients will be granted access to the Headspace intervention. There will also be the option to complete paper versions if the situation arises that might need this option.

**Post-test:** Approximately 6 weeks after completing the baseline measures participants will complete a second battery of self-report questionnaires delivered online (the intervention can be completed in 30 days and as such most users are expected to have completed the intervention 6 weeks after baseline). If patients take longer than 6 weeks to complete the intervention they will be asked to complete questionnaires regardless. **Follow-up:** 3 months after the intervention participants will complete a third battery of self-report questionnaires. For post-test and follow-up, participants will be sent an email asking them to complete the questionnaires.

If participants have not completed questionnaires after approximately 2 weeks, they will receive additional email reminders and may be contacted as appropriate by a member of the research team as a gentle reminder. If completing paper versions of the questionnaires, a repeat questionnaire will also be sent out to non-responders within this time frame and followed up by the research team as appropriate.

Telephone interviews will be conducted for approximately 20-25 patients (depending on data saturation) between 1 week and approximately 6 weeks after the intervention to elicit in depth discussion on the experiences of taking part and the acceptability of the intervention. A purposive sample of participants (as detailed below) will be contacted by email to invite them to take part. A draft interview guide has been created (Appendix C). Participants will consent at the beginning of the study to be contacted by the research team regarding the option of taking part in a telephone interview. Those that agree to take part in the telephone interview will then be contacted by the researcher by phone who will take verbal consent for the telephone interview before commencing the interview. This will include taking consent for the interview to be audio recorded. They will go through the verbal consent points as detailed in the draft interview schedule.

# Data collection

*Quantitative:* Validated questionnaires will be administered at baseline, end of treatment and at 3 months post training will assess asthma-related quality of life (Asthma Quality of Life Questionnaire, AQLQ), asthma control (The Asthma Control Questionnaire, ACQ), anxiety and depression (The Hospital Anxiety and Depression Scale, HADS), enablement (The Patient Enablement Instrument, PEI), illness perceptions (Brief Illness Perception Questionnaire, B-IPQ), mindfulness (in line with recent 'two-pronged' acceptance/awareness conceptualisations of mindfulness we will use the Philadelphia Mindfulness Scale; PMS), as well as a measure of medication adherence (Medication Adherence Report Scale for Asthma (MARS-A) and 'acceptance and action' (AAQ-II)\_. Data access granted to us by Headspace also allows us to monitor intervention usage. Questionnaires will primarily be delivered online using the LifeGuide software.

*Qualitative:* Qualitative evaluation will involve telephone interview. A purposive sample of approximately 20 participants will be invited to take part, based on demographic data obtained at baseline. Maximum variation

sampling will be used to ensure a range of age, gender, ethnic background and those that completed the course and those that dropped out. Interviews will take place approximately between 1 week and 6 weeks after the end of the intervention to elicit in depth discussion on the experiences of taking part, the acceptability of the intervention and views on the study outcomes in order to inform future RCT. The interviews will be audio recorded with participant consent. The interview will be anonymised when transcribed. Any direct quotes used will not include any identifiable information. Participants will be reminded that they can change their mind about taking part in the study, can stop the interview at any time or decline to answer a question.

## Data analysis

*Quantitative:* We will monitor recruitment procedures, recruitment rates/uptake, adherence and attrition using descriptive statistics in order to determine the feasibility of using Headspace.

In line with previous research, it is predicted that there will be the improvement from baseline scores in quality of life (measured by AQLQ) in the intervention group compared to control, controlling for age and gender, although this will be guided by data analysis to inform future RCTs.

If appropriate, we will also undertake exploratory statistical analysis to examine differences between baseline and follow-up questionnaires within (and between) intervention and control groups. These will be analysed with repeated-measures mixed-model ANCOVA. Bivariate correlations and linear regression modelling will be used to determine if changes in self-report measures are related to changes in quality of life, changes in disease control, mindfulness dosage/practice habits, and to control for baseline traits.

*Qualitative:* A preliminary qualitative topic guide has been drafted (Appendix C) which will explore participant views on the acceptability/feasibility of the intervention, barriers and facilitators to taking part in the intervention and the study, and required level of additional support. A thematic analysis of interview data will be conducted to ensure an inductive approach. Repeated readings of transcripts and listening of recordings will assist familiarisation with the data and identification of initial codes, these will then be defined and guide analysis of the full data set. Using constant comparison, a technique derived from grounded theory transcripts will be compared within and between each other aiding the iterative search for themes, which will then be reviewed, defined and named.

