Alongside the primary quantitative analysis (recruitment, retention & response rate) participants will also be invited to take part in telephone-based qualitative interviews that will discuss their experiences of taking part (for example, were there any barriers that hindered intervention usage) and the acceptability of the intervention (can the intervention be improved for use in a specific asthma population). Further investigation will also examine the extent to which Headspace usage analysis is associated with symptom improvement – particularly measures of intervention engagement and adherence, and whether they could be improved and exploration of barriers and facilitators for a subsequent fully powered randomised controlled trial.

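### The between-arm AQLQ comparison names age and gender as covariates but not baseline AQLQ, which gives up precision at no saving; any statement of benefit should rest on the baseline-adjusted between-arm difference

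*Protocol*

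**What the plan says.** In the protocol's Data analysis section, the AQLQ prediction reads "it is predicted that there will be the improvement from baseline scores in quality of life (measured by AQLQ", and the comparison is made "in the intervention group compared to control, controlling for age and gender". The sentence ends with a qualification: "although this will be guided by data analysis to inform future RCTs". The Lay Summary also sets the change seen in the app arm (80 patients) against the usual-care arm (40).

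The next paragraph of Data analysis plans, where appropriate, "exploratory statistical analysis to examine differences between baseline and follow-up questionnaires within (and between) intervention and control groups". It adds: "These will be analysed with repeated-measures mixed-model ANCOVA". No covariates are listed for that model. The only other mention of baseline adjustment, "and to control for baseline traits", belongs to the sentence on correlations and regression of changes in self-report measures.

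Sample population and recruitment places the baseline questionnaires before randomisation. Data collection lists AQLQ and HADS among the measures taken at baseline, end of treatment and 3 months. The Summary identifies the main quantitative work: "Alongside the primary quantitative analysis (recruitment, retention & response rate".

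**The concern.** The protocol names the form of the outcome (improvement from baseline), the comparison (app against control) and the covariates (age and gender). Read as written, this is a change-score comparison adjusted for two demographic variables. The baseline value of the outcome is usually much more strongly related to the follow-up value than age or gender, and here it is already collected on everyone before allocation. Leaving it out of the covariates widens the confidence interval for no saving.

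The estimate matters even in a feasibility trial. The Aim includes estimating effectiveness, and the Summary wants information on outcome variability to support a definitive trial.

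A second, smaller point is that change is to be examined within each arm as well as between arms. A within-arm change is not a treatment effect. With twice as many patients in the app arm, a within-arm test there has more power than the same test in controls.

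**Working it through.** **The plan's own figure.** The only precision figure in the protocol concerns the response rate: 20% ± 7% with 120 patients. It reproduces: 1.96 × √(0.2 × 0.8 / 120) = 7.16 percentage points (95% level assumed). It does not bear on AQLQ, for which the protocol gives no SD, correlation or target difference.

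**Inputs.** From the protocol: 80 app and 40 control patients. Assumed: equal SD at baseline and follow-up (set to 1), correlation r between the two after allowing for age and gender, no dropout, and the small cost of estimating the baseline slope ignored. Since r is not given, a range is shown.

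**Precision of the between-arm difference.**
- Change score: variance = 2(1 − r) × (1/80 + 1/40)
- Baseline-adjusted: variance = (1 − r²) × (1/80 + 1/40)
- Ratio, adjusted to change score: (1 − r²) / [2(1 − r)] = (1 + r)/2, so the reduction is (1 − r)/2

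With √(1/80 + 1/40) = 0.194, the 95% half-width is 1.96 × SE. Power is for an assumed true difference of 0.5 SD, two-sided 5%.

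| r | Variance cut | Half-width, change score | Half-width, adjusted | Power, change score | Power, adjusted |
|---|---|---|---|---|---|
| 0.3 | 35% | 0.45 SD | 0.36 SD | 59% | 77% |
| 0.5 | 25% | 0.38 SD | 0.33 SD | 73% | 85% |
| 0.6 | 20% | 0.34 SD | 0.30 SD | 82% | 90% |
| 0.7 | 15% | 0.29 SD | 0.27 SD | 92% | 95% |
| 0.9 | 5% | 0.170 SD | 0.165 SD | near 100% | near 100% |

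In sample-size terms, 120 patients analysed with adjustment are worth 120/0.75 = 160 analysed by change score at r = 0.5, and 120/0.85 = 141 at r = 0.7.

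The direction does not depend on equal SDs. With baseline SD s₀ and follow-up SD s₁, the change-score variance exceeds the adjusted variance by (s₀ − r·s₁)², which is never negative.

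**Within-arm tests.** Suppose both arms truly improve by the same 0.2 SD, so there is no treatment effect. The SD of change is √[2(1 − r)]. By normal approximation, the chance of a significant improvement in an arm of n is 1 − Φ(1.96 − 0.2√n / SD of change).
- r = 0.5 (SD of change 1.00): 43% in the arm of 80 and 24% in the arm of 40. App only: 0.432 × (1 − 0.244) = 33%. Control only: 0.244 × (1 − 0.432) = 14%.
- r = 0.7 (SD of change 0.77): 64% and 37%. App only: 0.637 × (1 − 0.372) = 40%. Control only: 0.372 × (1 − 0.637) = 13.5%.
- With 60 per arm, each one-sided pattern would occur in 23% (r = 0.5) or 25% (r = 0.7). The asymmetry therefore comes from the unequal arm sizes.
- With no true change in either arm, the asymmetry disappears (2.4% each way).

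**The case against.** - **Baseline is not ignored.** It enters through the change score. This stands, and it is why the comparison above is with a change-score analysis and not with follow-up scores alone. What is missing is baseline AQLQ as a named covariate.
- **The repeated-measures model might already include it.** A reader might infer that this ANCOVA adjusts only for age and gender, with baseline as one of its repeated levels. The text does not say so. Age and gender appear in a separate sentence that states a prediction, and the ANCOVA's covariates are unlisted, so baseline is not excluded there. A mixed model that keeps baseline as an outcome but gives both randomised arms a common baseline mean would recover essentially the same precision.
- **The gain can be small.** It is 5% of variance at r = 0.9, and power at r = 0.7 moves only from 92% to 95%. This stands, and so does the absence of bias: randomisation protects the change-score estimate too.
- **Within-arm results are not the stated basis for benefit.** Additional exploratory hypotheses, Design and Data analysis all refer to a comparison with control. This also stands. The asymmetry misleads only if someone reads within-arm significance as a treatment effect, and it requires a shared true change.
- **The analysis is exploratory.** The primary quantitative questions are recruitment, retention and response, and 120 patients were chosen for response-rate precision. This lowers the severity but does not argue against a free improvement.

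**Conclusion.** The point holds as a minor, cost-free improvement. The covariates named for the between-arm AQLQ comparison omit baseline AQLQ. Relative to a change-score analysis, adding it cuts the variance of the difference by (1 − r)/2: 35%, 25%, 15% and 5% at r = 0.3, 0.5, 0.7 and 0.9. These sizes rest on an assumed r, equal SDs and complete data; neither analysis is biased.

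Three stronger readings are not supported:
- **The treatment effect will be diluted by averaging in the baseline.** This takes the between-group comparison to be a group main effect. The protocol describes comparing "differences between baseline and follow-up questionnaires within (and between) intervention and control groups", which points to a difference in changes.
- **The SD passed to the definitive trial will be less precisely estimated.** Its relative precision depends on degrees of freedom, about 1/√(2 × 118) = 6.5% with either analysis. Omitting baseline makes the residual SD larger, not less well estimated.
- **The plan invites false claims of benefit.** No section sets a significance rule for within-arm change or uses it to claim efficacy.

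**What to change.** In Data analysis:
- State that AQLQ and HADS anxiety will be compared between arms at the 6-week post-test and the 3-month follow-up, with the baseline score of that outcome added to age and gender as covariates. A mixed model with a common baseline mean across arms is an equivalent option.
- Report the adjusted between-arm difference with its 95% confidence interval at each time.
- State that any statement of benefit rests on that estimate, and that within-arm changes are reported descriptively (mean and SD) without tests.
- Make the covariates of the repeated-measures model explicit, so that it agrees with the AQLQ sentence.

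The cost is wording only. All the data needed are already collected, and sample size, visits and questionnaires are unchanged.

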The full traditional mindfulness training programme is often challenging for patients to complete - previous research (SPCR FR9: 273) has examined the feasibility of mindfulness training to patients attending the 'difficult asthma' clinic in Southampton. In focus groups patients reported (improvements in subjective anxiety, increased relaxation, improved breathing control). However, there were a number of methodological challenges presented even by the reduced 4-week (one session/week of approx. 1 hr) group mindfulness training, including difficulty recruiting patients due to lack of time to and willingness to attend practice sessions.

Digital interventions can reach populations with long-term conditions without requiring face-to-face contact, with positive effects reported across a range of guided practices (i.e. pre-recorded), allowing convenience to patients in terms of timing and situation. Such interventions, if clinically effective, are likely to be cost-effective due to the low associated delivery costs. Headspace is the highest-rated mindfulness-based app and has shown benefits in reducing anxiety and stress. However, it has yet to be evaluated in patients with long-term respiratory conditions. Our group has recently received funding to explore and develop personalised 'disease specific' psychological interventions for people with asthma (BA: SPCR Postdoctoral Fellowship Award) and the matched-funding opportunity provided by Headspace will allow an assessment of recruitment response rate, intervention retention, outcome measure feasibility (see below) and variability within outcomes in order to support a definitive trial.

120 consenting volunteers will complete validated and widely used measures of control and disease-specific quality of life (including the Asthma Control Questionnaire and Asthma Quality of Life Questionnaire) as well as questionnaire measures of mindfulness using validated questionnaire tools before and after taking part in the Headspace course (or before and after treatment as usual in the control group: 80vs.40). The course consists of 8 'sessions' lasting 10 minutes, in which users listen to a guided meditation practice. The course is available on computer and on mobile devices; users are able to listen to each session as many times as they want, with a new session being unlocked each day.

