# Additional exploratory hypotheses

- 1. Patients in the intervention group will show improvements in measures of anxiety and asthma-specific quality of life (vs. control group).
- 2. Improvements in anxiety and asthma-specific quality of life will be associated with changes in self-reported mindfulness.

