## Sample population and recruitment

120 eligible patients will be identified by their GP practices using specified inclusion and exclusion criteria to search the GP electronic patient database. If deemed eligible by the GP they will be invited to take part in the study via a letter from the GP (sample size enables detection of 20% response rate with confidence interval of

 $\pm$ 7%, to accurately inform a randomized controlled trial for an intervention with a similar target population). GP practices will also have the option to use Docmail to help with the mail out if they prefer. There may also be opportunistic recruitment by GPs and community pharmacists with leaflets and posters about the study being on display. There will also be the opportunity to put information about the study on the GPs website, electronic visual displays at the surgery or on the surgery website or their social media page if they wish (using the electronic version of the poster).

Recruitment will take place with the help of Wessex CRN (estimate of costings attached). We will contact approximately 6-10 GP services who are interested in taking part in the study. We will aim to recruit a spread of GP practices across both urban and rural locations with different socio-economic qualities and deprivation scores.

Given the nature of this research as a well-powered feasibility study, we will not aim to balance study recruitment across age, gender, and ethnicity but will explore this in post-hoc analysis. We will, however, purposively sample across age, gender, asthma severity and ethnicity in the qualitative process analysis.

Patients will be selected as meeting the eligibility criteria below by their GP, and will be posted a copy of the participant information sheet and details of how to sign up to the study online, along with email contact details of the study team should they have any further queries.

Participants will also be sent an optional freepost reply-form to send back to the study team should they not wish to take part with the option to provide some demographic details and a reason for declining to take part in the study. It will be made clear that this is optional and it is up to the participant whether they wish to send this information back to the research team.

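### The exploratory change-on-change correlations and regressions are not stated to be within, or adjusted for, randomised arm; if pooled, they mix the arm effect with the individual-level link that hypothesis 2 concerns

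*Protocol*

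**What the plan says.** Two exploratory hypotheses are listed under Additional exploratory hypotheses in the protocol. The first predicts an arm effect: "Patients in the intervention group will show improvements in measures of anxiety and asthma-specific quality of life (vs. control group"). The second predicts an association: "Improvements in anxiety and asthma-specific quality of life will be associated with changes in self-reported mindfulness".

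The method that fits the second is in Data analysis: "Bivariate correlations and linear regression modelling will be used to determine if changes in self-report measures are related to changes in quality of life". The same sentence goes on to changes in disease control and to "mindfulness dosage/practice habits, and to control for baseline traits". It does not name hypothesis 2, but the mindfulness scale is one of the self-report measures. Randomised arm is neither named as a covariate nor excluded, and the sentence does not say whether the arms are pooled.

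Two nearby statements matter. The predicted AQLQ improvement is to be assessed "in the intervention group compared to control, controlling for age and gender", so arm is explicit there. The exploratory comparisons of baseline with follow-up are introduced by "If appropriate, we will also undertake exploratory statistical analysis" and are to be made both within and between arms. Allocation is given in the Summary ("or before and after treatment as usual in the control group: 80vs.40"). The Lay Summary says that controls get the app only once their follow-up measures are in.

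**The concern.** A bivariate correlation has no covariates. Computed over all participants, it combines the relation between the two changes inside each arm with the difference between the arm means. Hypothesis 1 expects the outcome means to separate, and a mindfulness course can reasonably be expected to move mindfulness scores too. If both happen, the pooled correlation departs from zero without any tendency for the patients whose mindfulness rose most to be those who improved most.

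Controlling for baseline traits does not cure this. Under randomisation, arm is expected to be unrelated to baseline characteristics, so adjusting for them leaves the arm difference in place.

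What is at stake is the reading of hypothesis 2. On a pooled analysis it would tend to look supported because hypothesis 1 is true, and the two would no longer be separate evidence. The clause on dosage has a related problem: controls have no study usage before follow-up, so a pooled usage model would partly re-express arm.

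**Working it through.** **The plan's own figure.** The protocol gives no figure for these correlations. Its one precision statement concerns recruitment: "sample size enables detection of 20% response rate with confidence interval of" ±7%. It reproduces: 1.96 × √(0.2 × 0.8 / 120) = 0.0716, or about 7%. It says nothing about a correlation.

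**Inputs.**
- From the protocol: 80 app and 40 control patients, so p = 2/3 and p(1−p) = 2/9.
- Assumed, because the protocol gives none: a two-sided 0.05 test; shifts d1 and d2 in the two change scores, in within-arm SDs; dropout of 0% or 20%.
- Null examined: zero correlation within each arm.

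**Induced correlation.** Pooling the arms gives

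r = p(1−p)·d1·d2 / √[(1 + p(1−p)·d1²)(1 + p(1−p)·d2²)].

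- 0.3 SD on both: 0.0200 / 1.0200 = 0.020
- 0.5 SD on both: 0.0556 / 1.0556 = 0.053
- 0.75 SD on both: 0.1250 / 1.1250 = 0.111

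The sign is negative for raw HADS anxiety change, where improvement is a fall; the size is the same.

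**Critical value.** With n = 120, t(118) = 1.980, so the critical r = 1.980 / √(1.980² + 118) = 0.179. Each induced r lies below it. The effect is therefore a raised rejection rate, not a routine false finding.

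**Rejection rates.** Simulation, 20,000 runs, 80:40:

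| Shift on both scales | Induced r | Arms pooled | Arm included |
|---|---|---|---|
| 0.3 SD | 0.020 | 5.5% | 5.1% |
| 0.5 SD | 0.053 | 8.6% | 5.0% |
| 0.75 SD | 0.111 | 22.6% | 5.0% |

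Repeat simulations gave 5.5–5.6% at 0.3 SD, 8.4–8.7% at 0.5 SD and 22.7% at 0.75 SD. Fisher's z agrees for the last row: 0.1116 × √117 = 1.21, and the chance of exceeding 1.96 − 1.21 = 0.75 is about 22.6%.

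**Sensitivity.**
- Unequal shifts: 0.5 and 0.3 SD give 6.5%; 0.75 and 0.3 SD give 7.9%; 0.5 and 0.75 SD give 13.3%.
- With 20% dropout (64:32), 0.75 SD on both gives 19.2–19.5%.
- Larger shifts: 0.8 SD on both gives r = 0.125 and 27.3%; 1.0 SD on both gives r = 0.182 and 51.5%.

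**Where 0.75 SD comes from.** The Summary cites an N = 83 trial with p < .001 for quality of life and perceived stress. Assuming equal groups and a t-test, p = .001 corresponds to d of about 0.75. That trial ran an 8-week course against an educational control, and the protocol reports no mindfulness-score result from it. The mindfulness half of the 0.75/0.75 row therefore has no source in the document.

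**The case against.** The strongest reply is that the protocol is silent rather than wrong. It does not say that the correlations are pooled, it names regression beside them, and its list of controls does not exclude arm. The preceding text plans work within as well as between arms, and the dosage clause reads most naturally as an app-arm analysis. Covariate lists for exploratory models are commonly left to a statistical analysis plan, which is not shown here. Much of this stands. A reader might infer that the protocol commits to a pooled, unadjusted correlation as the sole test of hypothesis 2; the text does not support that. What remains is that the protocol chooses a method and names a type of control, and on the natural pooled reading that choice is affected by the trial's own predicted effect.

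A second reply is that hypothesis 2 claims only an association, and a pooled correlation does estimate a pooled association. This is fair. The false-positive rates above are relative to a within-arm null that the protocol does not state. The within-arm relation is nevertheless the one that adds anything to hypothesis 1.

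Third, the artefact is small unless both shifts are large. This also stands: at 0.3 SD or below the rate is near nominal.

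Fourth, a reader might take hypothesis 2 as the evidence that will shape an asthma-specific programme. The Lay Summary credits the study as a whole with that role, and the Summary places the question of how to improve the intervention with the interviews. No decision rule attaches to these correlations.

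**Conclusion.** The point holds as a minor clarification. The protocol should state that analyses relating change to change are conditioned on randomised arm, because pooling mixes the arm effect with the within-arm association.

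The size depends on shifts that the protocol does not give: from about 5.5% at 0.3 SD, through 8.6% at 0.5 SD, to 22.6% at 0.75 SD on both scales, against about 5% with arm included. These figures rest on zero within-arm correlation, 80:40 with complete data and a two-sided 0.05 test. A reader might take 22.6% as the expected error rate. It is an illustrative upper case, since nothing in the document supports a 0.75 SD shift in mindfulness.

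The analysis is exploratory and conditional. Recruitment, retention and response rate, which are the primary quantitative outcomes, are unaffected.

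**What to change.** In Data analysis, specify for hypothesis 2:

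- Regress follow-up AQLQ, and separately HADS anxiety, on change in mindfulness score, with randomised arm, the baseline value of the outcome and baseline mindfulness in the model.
- Report the arm-adjusted (within-arm) partial correlation with its confidence interval in place of a pooled bivariate correlation.
- Fit the dosage and practice-habit models in the app arm only, and say so.

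No new data are needed. Arm costs one degree of freedom. The two baseline terms cost one each, and the existing reference to baseline traits may already cover them. With 120 complete cases the model has five parameters including the intercept, leaving 115 residual degrees of freedom. The design, sample size and patient burden do not change.
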